4.3.2. Subject Enrollment Instructions

- Sites must reserve a slot in Theradex IWRS. Each site is allowed 1 slot reservations at a time with a 5 day guaranteed hold for each slot.
- Next, fax the following redacted documents for review:
 1. Latest clinic note
 2. Pathology report showing histologically confirmed diagnosis of multiple myeloma
 3. Documentation of measurable disease (defined by at least one of the following):
 - a. Serum monoclonal protein M-protein level ≥ 0.5 g/dL
 - b. Urinary M-protein excretion of ≥ 200 mg over a 24-hour period
 - c. Involved free light chain level ≥ 10 mg/dL, along with an abnormal free light chain ratio
- Fax to: [name]/[name] at [contact]. Include your contact information in the fax cover sheet.
- Each reservation will need to be authorized and approved by an MD Anderson designee prior to registering the patient in OPEN. Once the slot is approved in IWRS, you may proceed with registering your patient in OPEN.

There is a two-step process to enrollment in CTSU OPEN. The subject cannot be fully registered in CTSU OPEN without knowledge of the TP53 mutation status which is part of the **eligibility** criteria 3.2.2. However, a patient may begin Cycle 1 of therapy provided they meet all other eligibility criteria aside from criteria 3.2.2.

The two-step enrollment process is as follows:

- (1) Register in CTSU OPEN **Step 1 once slot is approved through Theradex IWRS** to obtain patient's unique study ID
- (2) Subject may begin Cycle 1 therapy after eligibility is established even if TP53 mutation

status is not yet known as per **eligibility** criteria 3.2.2

(3) Study site receives *TP53* results during Cycle 1 therapy (or before) with 2 possibilities below:

- a) If non-wild-type (WT) *TP53* results, the patient is withdrawn from protocol for not meeting eligibility criteria prior to cycle 2 therapy. The site will need to complete step 2 of OPEN to indicate the patient has failed eligibility.
- b) If wild-type (WT) *TP53* results meeting eligibility criteria, the patient can continue on protocol. The site will complete step 2 of OPEN to indicate that patient has met eligibility prior to commencing cycle 2 therapy.

4.4. General Guidelines

Following registration, subjects should begin protocol treatment within 14 days. Issues that would cause treatment delays should be discussed with the Principal Investigator. If a subject does not receive protocol therapy following registration, the subject's registration on the study may be canceled. The Study Coordinator should be notified of cancellations as soon as possible.

5. TREATMENT PLAN

5.1. KRT-232 (AMG 232) + Carfilzomib, Lenalidomide, and Dexamethasone (KRd)

This will be a two-part Phase 1 dose-escalation and exploratory dose-expansion study of KRT-232 (AMG 232) in combination with carfilzomib, lenalidomide, and dexamethasone (KRd) in relapsed and/or refractory *TP53* WT myeloma subjects with 1-3 lines of prior therapy. Part A will consist of a dose-escalation phase of KRT-232 (AMG 232) to assess its safety and tolerability and identify an MTD/tentative RP2D in combination with KRd. KRT-232 (AMG 232) dose will be assigned according to the dose level stated in Section 5.4. Please refer to Section 5.4 to KRT-232 (AMG 232) dose escalation. After the MTD has been established, Part B of the study will involve an exploratory-dose expansion study of a goal of 10 additional subjects with relapsed and/or refractory myeloma who will be enrolled at the tentative RP2D.

Due to the timely need to initiate treatment in relapsed myeloma, *TP53* mutation status at screening is NOT required prior to KRT-232 (AMG 232) dosing. However, subjects found to have *TP53* mutation and/or deletion from screening bone marrow biopsy will be removed from study after C1 and continue on standard-of-care KRd alone. Toxicity monitoring of such subjects removed from active therapy with KRT-232 (AMG 232) will continue as described in the Treatment Plan. During the dose-expansion phase, subjects removed from study after Cycle 1 based on the *TP53* mutation and/or deletion status will be replaced to ensure that a goal of 10 subjects with *TP53* wild-type status are enrolled in the dose-expansion cohort.

Treatment will be administered on an outpatient basis. Reported adverse events and potential risks are described in Section 7. Appropriate dose modifications are described in Section 6. No investigational or commercial agents or therapies other than those described below may be administered with the intent to treat the subject's malignancy.

5.2. KRT-232 (AMG 232) Administration

KRT-232 (AMG 232) will be administered QD for 7 days every 28 days (i.e., 7 consecutive days of dosing followed by 21 consecutive days off treatment).

For QD dosing, subjects should self-administer KRT-232 (AMG 232) with or without food, with a full glass of water. KRT-232 (AMG 232) should not be crushed, chewed, or dissolved in water. Subjects should not be re-dosed with KRT-232 (AMG 232) after vomited doses.

The subject will be requested to maintain a medication diary of each dose of medication. The medication diary will be returned to clinic staff at the end of each course (APPENDIX E).

5.3. Carfilzomib, Lenalidomide, and Dexamethasone Administration

Regimen Description					
Agent	Premedications; Precautions	Dose	Route	Schedule	Cycle Length
Carfilzomib	IV Hydration: 250 mL to 500 mL normal saline (250 mL/hr) prior to each dose for Cycle 1 (optional for subsequent cycles). Dexamethasone: 4 mg PO or IV administered 30 minutes to 4 hours prior to Days 1-2, Days 8-9, and Days 15-16 dose	20 mg/m ² on Cycle 1, Day 1 and Cycle 1, Day 2 in 50 mL D5W ^b 27 mg/m ² starting on Cycle 1, Day 8 and all subsequent doses in 50 mL D5W ^b	IV over 10-30 minutes (allowable window of +10 minutes)	Cycles 1-12: Days 1-2, 8-9, 15-16 for Cycles 1-12. Cycles 13-18: Days 1-2, 15-16.	28 days (4 weeks)

	Ondansetron (optional) 8 mg IV or PO 30 minutes prior to each dose				
Lenalidomide	Can be taken with or without food. capsules should be swallowed whole with water and capsules should not be opened, broken, or chewed.	25 mg	Oral	Days 1-21	
Dexamethasone	None	40 mg	Oral or IV	Days 1, 8, 15, and 22	

^aPremedication with dexamethasone 4 mg is required before each carfilzomib dose during Cycle 1 and is optional for subsequent cycles. During Cycle 1 and if pretreatment dexamethasone is necessary beyond Cycle 1, the treatment dose of dexamethasone 40 mg IV or PO will be given 30 minutes to 4 hours prior to each carfilzomib dose on Days 1, 8, and 15 which will serve as both the pretreatment and treatment dose of dexamethasone.
^bCalculate carfilzomib dose using the patient's actual body surface area at baseline. In patients with a body surface area greater than 2.2 m², calculate the dose based upon a body surface area of 2.2 m².

Doses of lenalidomide or oral dexamethasone that are skipped or vomited will not be made up.

5.4. KRT-232 (AMG 232) + Carfilzomib, Lenalidomide, and Dexamethasone Treatment Plan

Dose Regimen

KRT-232 (AMG 232) + carfilzomib, lenalidomide, and dexamethasone will be administered per the following schedule:

Cycles 1-12 (28 day cycle)

- KRT-232 (AMG 232) once daily by mouth 7 out of 28 days
- Carfilzomib 20 mg/m² IV on Days 1 and 2 of Cycle 1, escalating to 27 mg/m² IV on Days 8, 9, 15, 16 of Cycle 1 and continuing on Days 1, 2, 8, 9, 15, 16 of Cycles 2 through Cycle 12
- Lenalidomide 25 mg PO on Days 1-21
- Dexamethasone 40 mg PO or IV on Days 1, 8, 15, and 22

Cycles 13-18 (28 days each)

- KRT-232 (AMG 232) once daily by mouth 7 out of 28 days
- Carfilzomib 27 mg/m² IV on Days 1, 2, 15, and 16
- Lenalidomide 25 mg PO on Days 1-21
- Dexamethasone 40 mg PO or IV on Days 1, 8, 15, and 22

Cycles 19+ (28 days each)

- KRT-232 (AMG 232) once daily by mouth 7 out of 28 days
- Lenalidomide 25 mg PO on Days 1-21
- Dexamethasone 40 mg PO or IV on Days 1, 8, 15, and 22

Part A (Dose-escalation scheme)

The MTD is defined as the highest dose at which six subjects have been treated and less than two subjects experienced DLT within the first cycle of treatment in Phase I of the trial. To determine the MTD, escalation for KRT-232 (AMG 232) will be conducted following the “3+3” design with de-escalation. A cohort of three subjects will be treated at the starting dose level and observed until the end of the first cycle (subjects non-evaluable for DLT will be replaced). The dose level will be escalated with each new cohort until at least one out of three subjects of a cohort experiences DLT. If one subject experiences a DLT, then three additional subjects will be treated at the same dose level; if none of the three additional subjects experiences a DLT, then the dose escalation will be continued by treating the next cohort of three subjects at the next higher dose level. If at least two out of up to six subjects at a dose level experience a DLT, the MTD will be considered to have been exceeded, and up to 3 more subjects will be treated at the next lower dose if there are less than 6 subjects already treated at that dose. The dose steps for escalation are displayed below:

Dose Escalation Schedule	
Dose Level	Dose of KRT-232 (AMG 232)*
- 1	30 mg/day PO x 7 days out of 28 day cycle
+ 1	60 mg/day PO x 7 days out of 28 day cycle
+ 2	90 mg/day PO x 7 days out of 28 day cycle
+ 3	120 mg/day PO x 7 days out of 28 day cycle
+ 4	180 mg/day PO x 7 days out of 28 day cycle
+ 5	240 mg/day PO x 7 days out of 28 day cycle

If dose-de-escalation is needed for Dose level 1, Dose level -1 is defined as 30 mg/day x 7 days out of 28 day cycle.

There should be no dose modifications of KRT-232 (AMG 232) and KRd during the DLT-evaluable period (Cycle 1). Subjects requiring dose-reductions during the DLT-evaluable period will be considered a DLT.

Part B (Dose-expansion scheme)

After determination of the KRT-232 (AMG 232) MTD or proven tolerability of the highest planned dose, and a goal of 10 additional subjects will be treated in the Part 2 dose expansion in combination with KRd. The primary objective of this dose-expansion phase is to confirm the safety and tolerability of KRT-232 (AMG 232) + KRd at the MTD and tentative RP2D in a goal

of 10 subjects with relapsed and/or refractory multiple myeloma. The tentative RP2D will be determined based on the review of safety data at the MTD.

During the dose-expansion phase, subjects removed from study after Cycle 1 based on the *TP53* mutation and/or deletion status will be replaced to ensure that a goal of 10 subjects with *TP53* wild-type status are enrolled in the dose-expansion cohort.

The subject will be requested to maintain a medication diary of each dose of medication. The medication diary will be returned to clinic staff at the end of each course.

KRT-232 (AMG 232)

The following medications and/or therapies should not be administered within the timeframes specified prior to enrollment and during the study (unless otherwise specified below):

- Antitumor therapy (chemotherapy, antibody therapy, molecular targeted therapy, retinoid therapy, hormonal therapy, or investigational agent) within 21 days of study day 1; concurrent use of hormone deprivation therapy for hormone-refractory prostate cancer or breast cancer and continuation of previous hormone therapy in breast cancer subjects are permitted.
- Treatment with immune modulators including, but not limited to, corticosteroids, cyclosporine and tacrolimus within 3 weeks prior to enrollment, except for a corticosteroid dose equivalent to dexamethasone of ≤ 4 mg/day
- Therapeutic or palliative radiation therapy within 4 weeks of KRT-232 (AMG 232) day 1.
- All herbal medicines (e.g., St. John's wort), vitamins, and supplements consumed by the subject within the 30 days prior to receiving the first dose of KRT-232 (AMG 232), and continuing use, if applicable, will be reviewed by the Principal Investigator and the sponsor.
- Use of any known CYP3A4 substrates with narrow therapeutic window (such as alfentanil, astemizole, cisapride, dihydroergotamine, pimozide, quinidine, sirolimus, or terfanide) within the 14 days prior to receiving the first dose of KRT-232 (AMG 232). Other medications (such as fentanyl and oxycodone) may be allowed per investigator's assessment/evaluation.
- Use of any known CYP2C8 substrates with a narrow therapeutic window within the 14 days prior to receiving the first dose of KRT-232 (AMG 232)
- Treatment with medications known to cause QTc interval prolongation within 7 days of study day 1 unless approved by the sponsor. Use of ondansetron is permitted for treatment of nausea and vomiting. Systemic anticoagulation therapy, with warfarin, direct thrombin inhibitors, indirect thrombin inhibitors and direct factor Xa inhibitors, within 14 days or 5 half-lives (whichever is longer) of day 1. Low molecular weight heparin and prophylactic low-dose warfarin are permitted.
- Autologous stem cell transplantation at least 12 weeks prior to starting KRT-232 (AMG 232) + KRd
- Allogeneic stem cell transplantation at least 24 weeks prior to starting KRT-232 (AMG 232) + KRd, and these subjects must also NOT have moderate to severe active acute or

chronic graft versus host disease (GVHD).

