2.7.2. Pharmacokinetic and Pharmacodynamic Studies

Macrophage inhibitor cytokine-1 (MIC-1)

MIC-1, a secreted p53 transcriptional target, will be evaluated as an integrated pharmacodynamic biomarker for p53 pathway activation in response to MDM2 inhibition in this study. In preclinical studies, increases in MIC-1 levels were observed *in vitro* and *in vivo* in response to doxorubicin treatment, and correlated with increases in other downstream markers of p53 pathway activation (Yang et al., 2003).

In a clinical study with the MDM2 inhibitor RG7112 in liposarcoma, serum MIC-1 was been assessed as a pharmacodynamic marker using an ELISA at different time points and correlated with drug exposure levels of the study drug (Ray-Coquard et al., 2012). In preliminary analyses of clinical trial data, there was an exposure-response correlation observed between changes in serum MIC-1 levels and KRT-232 (AMG 232) exposure (both maximal (C_{max}) and total exposure (AUC) (KRT-232 (AMG 232) Investigators Brochure Date: 08 Dec. 2015).

In this study, serum MIC-1 testing will be performed using an ELISA-based assay at the ETCTN central laboratory of [name] at Johns Hopkins University. For serum MIC-1 levels, each individual level will be normalized to the baseline level for that subject collected prior to KRT-232 (AMG 232) dosing.

KRT-232 (AMG 232) pharmacokinetic profile

These studies are necessary to characterize the exposure to KRT-232 (AMG 232). KRT-232 (AMG 232) is an orally bioavailable MDM2 inhibitor. In cancer subjects, KRT-232 (AMG 232) exposure is dose proportional over the dose range proposed in this LOI (KRT-232 (AMG 232)

Investigators Brochure Date: 08 Dec. 2015). [REDACTED]

In this protocol, KRT-232 (AMG 232) will be combined with carfilzomib, lenalidomide, and dexamethasone. Carfilzomib is primarily inactivated by peptidases and hydrolysis with minor contributions by CYP450 isozymes (specific isozyme not listed). Lenalidomide is not metabolized by CYP450 but is a P-glycoprotein substrate. Dexamethasone is metabolized by CYP3A4 but does not have a narrow therapeutic window. Therefore concerns of a drug-drug interaction are minimal with the combination. Other narrow therapeutic window drugs predominantly cleared by CYP2C8 and/or CYP3A4 will be excluded.

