- d) Allogeneic stem cell transplantation at least 24 weeks prior to starting KRT-232 (AMG 232) + KRd, and these subjects must also NOT have moderate to severe active acute or chronic graft versus host disease (GVHD).

3.1.6. Subjects must be ≥ 18 years old. Because no dosing or adverse event data are currently available on the use of KRT-232 (AMG 232) in combination with KRd, subjects < 18 years of age are excluded from this study.

3.1.7. Subjects must have ECOG performance status ≤ 2 (Karnofsky $\geq 60\%$, see Appendix A).

3.1.8. Subjects must have normal organ and marrow function as defined below:

- a) Absolute neutrophil count (ANC) $\geq 1,000/\text{mcL}$ without growth factors within 2 week of initiation of treatment
- b) Platelets $\geq 50,000 \text{ cells/mm}^3$ if marrow plasmacytosis $< 50\%$ OR platelet count $\geq 30,000 \text{ cells/mm}^3$ if marrow plasmacytosis $\geq 50\%$.
- c) Hemoglobin $\geq 8 \text{ g/dL}$ within 2 weeks of the initiation of treatment
- d) Total bilirubin $< 1.5 \times$ institutional upper limit of normal (ULN) ($< 2.0 \times$ ULN for subjects with documented Gilbert's syndrome or $< 3.0 \times$ ULN for subjects for whom the indirect bilirubin level suggests an extrahepatic source of elevation)
- e) AST(SGOT)/ALT(SGPT) $\leq 2.5 \times$ ULN
- f) Alkaline phosphatase $< 2.0 \times$ ULN (if liver or bone disease are present, $< 3.0 \times$ ULN)
- g) Creatinine clearance (eGFR) $\geq 50 \text{ mL/min}/1.73 \text{ m}^2$

3.1.9. Subjects must have adequate coagulation laboratory assessments, as follows:

Prothrombin time (PT) or partial thromboplastin time (PTT) $< 1.5 \times$ upper limit of normal (ULN), OR International normalized ratio (INR) < 1.5 .

3.1.10. Subjects who have received radiation therapy targeting $> 10\%$ of the bone marrow space must have completed this at least 2 weeks prior to starting therapy with KRT-232 (AMG 232) + KRd.

3.1.11. Subjects must be able and willing to provide bone marrow biopsies/aspirates and buccal swab as requested by the protocol.

3.1.12. Subjects must be willing to undergo myeloma genotyping for *TP53* mutation, insertion, or deletion at screening.

3.1.13. Subjects must have an estimated life expectancy of at least 3 months.

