- 3.2.8. Subjects' medication list such a herbal medicines (*e.g.*, St. John's wort), vitamins, and supplements will be reviewed before starting first dose of KRT-232 (AMG 232) and at each clinic visit. Any potential drug interactions will be brought and discussed with the Principle Investigator. Use of any known CYP3A4 substrates with narrow therapeutic window (such as alfentanil, astemizole, cisapride, dihydroergotamine, pimozide, quinidine, sirolimus, or terfanide) within the 14 days prior to receiving the first dose of KRT-232 (AMG 232) is not permitted. Other medications (such as fentanyl and oxycodone) may be allowed per investigator's assessment/evaluation.
- 3.2.9. Treatment with medications known to cause QTc interval prolongation within 7 days of study day 1 is not permitted unless approved by the sponsor. Use of ondansetron is permitted for treatment of nausea and vomiting.

- 3.2.10. Current use of warfarin, factor Xa inhibitors and direct thrombin inhibitors.
Note: Low molecular weight heparin and prophylactic low dose warfarin are permitted. PT/PTT must meet the inclusion criteria. Subjects taking warfarin must have their INR followed closely.
- 3.2.11. Uncontrolled intercurrent illness including, but not limited to, ongoing or active infection, symptomatic congestive heart failure, unstable angina pectoris, cardiac arrhythmia, or psychiatric illness/social situations that would limit compliance with study requirements.
- 3.2.12. Subjects with myocardial infarction within 6 months of study day 1, symptomatic congestive heart failure (New York Heart Association (NYHA) Class III and higher), unstable angina, or cardiac arrhythmia requiring medication are excluded.
- 3.2.13. Subjects with GI tract disease causing the inability to take oral medication, malabsorption syndrome, requirement for intravenous alimentation, prior surgical procedures affecting absorption, uncontrolled inflammatory GI disease (e.g., Crohn's disease, ulcerative colitis).
- 3.2.14. Subjects with history of bleeding diathesis.
- 3.2.15. Subjects with active infection requiring IV antibiotics within 2 weeks of study enrollment (day 1) are excluded.

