5.8. General Concomitant Medication and Supportive Care Guidelines

5.8.1. Concomitant Medications

Because there is a potential for interaction of KRT-232 (AMG 232) with other concomitantly administered drugs, the case report form must capture the concurrent use of all other drugs, over-the-counter medications, or alternative therapies. The Principal Investigator should be alerted if the subject is taking any agent known to affect or with the potential for drug interactions. The principal investigator should be notified if the subject is taking CYP3A4 substrates with narrow therapeutic window (such as alfentanil, astemizole, cisapride, dihydroergotamine, pimozide, quinidine, sirolimus, or terfanide) or any known CYP2C8 substrates with a narrow therapeutic window while receiving AMG232.

A patient drug information leaflet and wallet card for the potential drug-interactions will be provided to each subject as referenced in Appendix B.

As noted in section 3.2.9, for treating emesis, other medications (such as fentanyl and oxycodone) may be allowed per investigator's assessment/evaluation. The study team should check a frequently-updated medical reference for a list of drugs to avoid or minimize use of.

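### The radiotherapy washout differs in length and scope between Section 5.4 and inclusion criterion 3.1.10, so a subject can be eligible and still breach the treatment plan

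*Combined protocol and SAP*

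**What the plan says.** **Radiotherapy.** Criterion 3.1.10, repeated as item 10 of the synopsis inclusion list, concerns subjects who have had radiotherapy to more than 10% "of the bone marrow space must have completed this at least 2 weeks prior to starting therapy with KRT-232 (AMG 232) + KRd". No other item in Section 3 sets a radiotherapy washout. The list under the KRT-232 heading in Section 5.4 opens by saying that the named therapies "should not be administered within the timeframes specified prior to enrollment and during the study (unless otherwise specified below". One entry is "Therapeutic or palliative radiation therapy within 4 weeks of KRT-232 (AMG 232) day 1". No radiotherapy exception follows it.

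**CYP2C8 substrates.** Section 2.7.2 states: "Other narrow therapeutic window drugs predominantly cleared by CYP2C8 and/or CYP3A4 will be excluded". Section 5.4 lists "Use of any known CYP2C8 substrates with a narrow therapeutic window within the 14 days prior to receiving the first dose". Exclusion 3.2.8, like synopsis exclusion 8, covers only "Use of any known CYP3A4 substrates with narrow therapeutic window". Section 5.8.1 asks that the principal investigator be told if a subject takes certain CYP3A4 substrates "or any known CYP2C8 substrates with a narrow therapeutic window while receiving AMG232".

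**Anticoagulants.** Exclusion 3.2.10 is framed as use at the time of entry. Section 5.4 sets a washout of 14 days or 5 half-lives, whichever is longer. Both allow low molecular weight heparin and prophylactic low-dose warfarin.

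**Registration.** Section 4.3.1 tells site staff to confirm, before using OPEN, that every eligibility criterion has been met. The documents requested for slot approval in Section 4.3.2 are a clinic note, a pathology report and evidence of measurable disease. Neither section mentions the 5.4 list.

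**The concern.** The 5.4 list governs the time before enrollment, so it acts as a second set of entry rules, yet it sits outside the criteria that are checked at registration. Several of its entries repeat Section 3 windows: 21 days for antitumor therapy, 3 weeks for corticosteroids, 14 days for CYP3A4 substrates, 7 days for QTc-prolonging drugs, and 12 and 24 weeks for transplantation. Where the two sets differ, the difference therefore reads as drafting drift rather than a deliberate extra layer.

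What is at stake is the definition of the population in which DLTs are counted. Escalation turns on one or two events in three to six subjects. Section 2.6 gives overlapping toxicity, thrombocytopenia in particular, as the reason for the cautious starting dose, and Section 5.6 includes neutropenia and thrombocytopenia among the DLTs. If one site applies 3.1.10 and another 5.4, subjects with different recent marrow exposure enter the same cohort. The DLT-evaluable set in Section 13.1.4 has no provision for subjects who met the criteria but breached 5.4, so they would be counted. Whether they are protocol deviations cannot be settled from the text.

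**Working it through.** The plan gives no figure to reproduce here. The check sets the rules side by side and finds the subjects on whom they disagree.

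**Step 1. The radiotherapy rules.** Let *d* be the number of days from the end of radiotherapy to day 1. Two weeks is 2 × 7 = 14 days and four weeks is 4 × 7 = 28 days. I read a restriction within 4 weeks as *d* under 28.

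| | 3.1.10 and synopsis inclusion 10 | 5.4 list |
|---|---|---|
| Over 10% of marrow space | *d* ≥ 14 | *d* ≥ 28 |
| 10% of marrow space or less | no washout | *d* ≥ 28 |
| Counted back from | start of KRT-232 + KRd | KRT-232 day 1 |
| Exception stated | none | none for radiotherapy |

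**Step 2. Do different anchor dates explain the gap?** No. The study calendar starts KRT-232, carfilzomib, lenalidomide and dexamethasone together on Cycle 1 Day 1, so both clocks run from the same day.

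**Step 3. Who meets Section 3 but breaches 5.4?**
- Over 10% of marrow: 14 ≤ *d* < 28, that is 14 to 27 days before day 1, a span of 28 − 14 = 14 days.
- 10% of marrow or less: any *d* under 28, the full 28 days.

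The mismatch is thus in scope as well as length, and it is wider for smaller fields.

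**Step 4. Does another passage decide between them?** None states that 5.4 overrides Section 3 or the reverse. The opening of the 5.4 list allows exceptions only if they are given there.

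**Step 5. CYP2C8.** Sections 2.7.2 and 5.4 agree that narrow-window substrates are to be kept out. Criterion 3.2.8 does not permit them; it leaves them unmentioned, as does every other item in 3.1 and 3.2. Once treatment has begun, 5.8.1 asks for notification. This is an omission from the criteria, not two competing values.

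**Step 6. Anticoagulants.** A subject who has stopped a listed anticoagulant but is still inside the 5.4 washout is outside the wording of 3.2.10 and inside the restriction in 5.4. The two texts need the same window.

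**The case against.** The best defence is that both radiotherapy rules can be met together, since any subject who satisfies the longer one satisfies both. The 5.4 wording is also advisory in tone, and Section 4.3.1 does not name Section 3 when it refers to eligibility. All of this is true. It does not remove the problem: a site that checks the eligibility criteria correctly can still register a subject who breaches 5.4, and nothing tells it to look there. Section 4.3.2 cites eligibility by its Section 3 number, which supports reading Section 3 as the list that is checked.

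The defence is stronger on the secondary points. For CYP2C8, 3.2.8 already requires a medication review before the first dose and discussion of possible interactions with the investigator. For anticoagulants, the longer window again satisfies both texts, and 3.1.9 and 3.2.14 separately address coagulation and bleeding risk. These are alignment points, not contradictions of the same weight.

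A reader might infer that interacting drugs admitted through these gaps would raise the DLT count. The documents do not support that for CYP2C8. Section 8.1 says KRT-232 is not metabolized by CYP450 enzymes and describes it as the inhibitor, so by this route the substrate is the drug affected. It also reports no identified interaction potential for CYP enzymes other than CYP3A4.

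A reader might also infer a measurable loss in the probability of passing a dose level. The documents give neither a DLT risk for recently irradiated subjects nor their number, so any such figure would only reflect an assumed risk. Existing safeguards also weaken the link: neutrophil and platelet minimums in 3.1.8, recovery from earlier toxicity in 3.2.3, persistence requirements in several hematologic DLTs, and the exclusion of events with a clear alternative cause.

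**Conclusion.** Wrong as written for radiotherapy. The two rules disagree for subjects irradiated to more than 10% of marrow 14 to 27 days before day 1, and for those irradiated to a smaller field at any time under 28 days. This rests on reading both clocks from Cycle 1 Day 1 and on the absence of any statement of precedence.

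The CYP2C8 omission and the anticoagulant difference are real but secondary. The consequence is uncertainty about who may enter small DLT cohorts and about which registered subjects are deviations. No sample size, confidence interval width or other operating characteristic in the plan is affected. The number of subjects concerned cannot be derived from the documents.

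**What to change.** Reconcile the Section 5.4 list with 3.1.10, 3.2.8 and 3.2.10, the matching synopsis items (inclusion 10; exclusions 8 and 10), and Sections 2.7.2 and 5.8.1. Each restriction should have one window, one reference date and one scope, including whether field size matters for radiotherapy. State it in the eligibility criteria checked at registration, and let 5.4 refer back to the criteria instead of restating them. If a restriction applies only during treatment, say so, and say whether it is a prohibition or a duty to notify. Which window and scope to keep is a clinical decision on which this review takes no position.

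The cost is amendment wording and an update to the registration check. Depending on the window kept, a few candidates may have to wait or may be excluded. If the amendment comes after enrollment has begun, subjects already entered should be checked against both texts, so that their deviation status is recorded consistently.
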